2. RATIONALE						
3. THEORETICAL FRAMEWORK						
4. RESEARCH QUESTION/AIM(S)						
5. STUDY DESIGN/METHODS						
6. STUDY SETTING						
7. SAMPLE AND RECRUITMENT						
8. ETHICAL AND REGULATORY COMPLIANCE						
9. DISSEMINATION POLICY						
10. REFERENCES						
11. APPENDICES						

KEY STUDY CONTACTS

Chief Investigator	[name]				
	[contact]				
	[contact]				
Study Co-ordinator	CI above will cover these duties				
Sponsor	University Hospital Southampton NHS Foundation Trust [name]				
	University Hospital Southampton NHS Foundation Trust				
	[name]				
	Southampton				
	[name]				
	[contact]				
	[contact]				
Joint-sponsor(s)/co-sponsor(s)	n/a				
Funder(s)	NIHR				
Key Protocol Contributors	[name]: [contact]				
	[name]: [contact]				
Committees	The PPI Advisory Group is established. The Study Steering Committee will be in place by end of February 2025				

STUDY SUMMARY

Study Title	Improving the care people with learning disabilities receive in hospital: an ethnographic study examining the experiences of people with learning disabilities and the organisation and delivery of their care
Internal ref. no. (or short title)	Care4Me
Study Design	This project will use ethnography (with 8 case study adults with learning disabilities and carers (estimated n=16-24) and staff (estimated n=64) involved in their care, using observation, interviews, document analysis) to understand how care is experienced by adults with learning disabilities and how it is organised and delivered by ward teams during a hospital admission.
Study Participants	Adults with learning disabilities who are admitted within two large general hospitals in England over a four-month period. We will include a range of participants who have had particular types of experiences (critical case sampling) to

	ensure we include people with learning disabilities who are typically excluded from research. Sampling will include adults with a learning disability who represent a range of factors that may influence care delivery, and where possible, sociodemographic factors: - Severity of learning disability (mild to profound) - Primary reason for the admission, including planned and unplanned admissions People from Black, Asian, and Minority Ethnic groups with a learning disability Expected length of stay - To include people attending hospital with differing levels of support, who have a full-time family or professional carer, and who have limited or no support.				
Planned Size of Sample (if applicable)	8 adults with learning disabilities (4 per hospital) Anticipated 16-24 carers Anticipated 64 members of hospital staff Total sample size = 96				
Follow up duration (if applicable)	n/a fieldwork will be carried out during their hospital				
Tollow up duration (if applicable)	admission.				
Planned Study Period	September 2024-March 2026				
Research Question/Aim(s)	This exploratory ethnographic study will examine the experiences of adults with learning disabilities and the organisation and delivery of their care during a hospital admission. Our objectives: 1. Understand care experiences from the perspectives of adults with learning disabilities and their family carers during a hospital admission, including people with complex needs and profound learning disabilities. 2. Examine how care is organised and delivered for adults with learning disabilities during a hospital admission including how ward teams understand and respond to their needs. 3. Use the findings to co-design guidance with adults with learning disabilities, their carers and ward staff to deliver initial strategies to improve support for adults with learning disabilities at the ward level during hospital admissions.				

FUNDING AND SUPPORT IN KIND

FUNDER(S) (Names and contact details of ALL organisations providing funding and/or support in kind for this study)	FINANCIAL AND NON FINANCIALSUPPORT GIVEN
NIHR	£148,994.00

ROLE OF STUDY SPONSOR AND FUNDER

The Sponsor is University Hospital Southampton NHS Foundation Trust (UHS), which is the organisation that is taking legal responsibility for the research project.

NIHR has carried out a rigorous peer review of the study prior to funding approval. All requirements of an NIHR contract will be met, including provision of 6 month progress reports and the delivery of progress milestones as required.

The CI (JH) controls the final decision in study design, conduct, data analysis and interpretation, manuscript writing, and dissemination of results.

ROLES AND RESPONSIBILITIES OF STUDY MANAGEMENT COMMITEES/GROUPS & INDIVIDUALS

Steering committee: The study steering committee will be in place by end of February 2025. This is required by the NIHR and fulfills the role described in their guidance (https://www.nihr.ac.uk/documents/research-governance-guidelines/12154):

The role of the Steering Committee is to provide overall supervision for a project on behalf of the study's Sponsor and Funder and to ensure that it is conducted to the rigorous standards set out in the UK Policy Framework for Health and Social Care and the Guidelines for Good Clinical Practice.

The role of the Study Steering Committee is as follows:

- To provide advice, through its Chair, to the study's funder, sponsor, Chief Investigator, host institution, and contractor
- To concentrate on the study's progress, adherence to the protocol, and patient safety (where appropriate), and to consider new information of relevance to the research question

- To uphold the rights, safety and well-being of the participants: these are the most important considerations and should prevail over the interests of the research
- To ensure appropriate ethical and other approvals are obtained in line with the project plan
- To agree proposals for substantial protocol amendments and provide advice to the sponsor and funder regarding approvals of such amendments
- · To provide advice to the investigators on all aspects of the study

PPI advisory groups: Our PPI Advisory Groups of people with learning disabilities (Treat Me Well at Southampton Mencap and Southern Health's Patient Experience group) and carers are already established. Representatives (a person with a learning disability and a family carer) from the above Advisory Groups are co-applicants. The lead researcher has spent two days with a public contributor with a profound learning disability to learn about how this person communicates, their needs and what is important to them, which has been used to inform how involvement in our research could be improved for people with profound learning disabilities. We are paying for PPI contributors' time using NIHR PPIE rates.

A summary of PPI activities

- MB and AI will meet with the other co-applicants monthly except during the fieldwork phase (March-June 2025)
- Months 1-3 JH will identify and spend a total of two days with a person with profound and multiple learning disabilities and their carer(s), learning how they communicate including assent, dissent and distress.
- The PPI Advisory Groups with people with learning disabilities will meet monthly (except during
 the first two months of fieldwork) to ensure they are fully involved. This ensures they will have
 adequate time to be fully involved in the research design, implementation, analysis, and output
 development. We will meet with the carers' group every two months as their availability and
 support needs will be lower. Activities will be:
- Month 1: Agree terms and support required
- Month 2: Agree key principles for recruitment and accessible project materials
- Month 3-4: Test and critique accessible materials created by FL (PPI Lead)
- Months 5-6: Discuss responses to REC, develop toolkit for accessible interviews
- Month 9: Discuss initial findings and develop third order coding
- Months 9-18: co-design sessions to create outputs

JH and FL will support a PPI member with a learning disability to develop and present research findings at a conference (preference given to MB).

PROTOCOL CONTRIBUTORS

The Sponsor (University Hospital Southampton NHS Foundation Trust (UHS) is the organisation that is taking legal responsibility for the research study.

The funder NIHR has carried out a peer review of the study prior to awarding funding. All requirements of an NIHR contract will be met, including provision of 6 month progress reports and the delivery of progress milestones as required.

The PI (JH) is responsible for the design, conduct, data analysis and interpretation, manuscript writing, and dissemination of results.

This protocol has been developed in collaboration with people with learning disabilities and their carers. This includes the Treat Me Well group (Southampton Mencap), which includes people with severe learning disabilities, our carers group and our co-applicant, Al and staff at Southampton Mencap.

People with learning disabilities described their significant anxieties and fear of hospital care. They felt excluded from decision making and had been asked to sign forms they did not understand. They said staff spoke too fast for them to understand, long waits made them anxious, they were afraid of needles and cannulas after bad experiences. They identified pain management, eating and drinking and vital signs (particularly anxiety/discomfort around the use of blood pressure cuffs) as important research priorities.

Family carers told us that they do all of the basic care but it is difficult to get their concerns taken seriously. They felt they had to take a hands-on approach to care and be available 24-7 as advocates and could be excluded from providing support when their son or daughter had requested it (e.g. during an MRI scan).

This has informed the research focus and the methods we are using, including our informed consent approaches and our approach to co-production. This includes the use of EasyRead, Photosymbols, Widgit symbols, simple language, providing questions ahead of time, use of graphics, role play scenarios and stories, embedded throughout the design of this study and in the PPI work.

KEY WORDS: Hospital, learning disabilities, nursing, ward care, reasonable adjustments, ethnography.

STUDY FLOW CHART

	Sep-	Oct-	Nov-	Dec-	Jan-	Feb-	Mar-	Apr-	May-	Jun-	Jul-	Aug-	Sep-	Oct-	Nov-	Dec-	Jan-	Feb-	Mar-
	24	24	24	24	25	25	25	25	25	25	25	25	25	25	24	25	26	26	24
Project setup																			
Write HRA application																			
Co-applicant meetings																			
Negotiate local site approvals																			
Development of accessible materials & review by advisory groups																			
Pre-fieldwork PPI group meetings (TMW & SHPEG)																			
Pre-fieldwork PPI advisory group (carers)																			
Submit HRA application																			i
Respond to REC/HRA changes																			
Ethnographic fieldwork across two sites																			
Analysis																			
Analysis discussion and co-design process with PPI groups (people with learning disabilities and carers) & staff																			
Draft and submit final report																			
Dissemination of outputs																			

Commented [JH1]: I have amended as agreed with our grant manager for spending longer on PPI and writing application

STUDY PROTOCOL

Improving the care people with learning disabilities receive in hospital: an ethnographic study examining the experiences of people with learning disabilities and the organisation and delivery of their care

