-Ethnographic in situ short interviews with ward staff attending the bedside (approximately 8 per case study) and directly caring for participants to explore how they understand the participant's care and communication needs.

- -Documentary examination of hospital passport and medical records to examine care across the admission and how it is recorded.
- -Ward level documentation on staffing levels and patient acuity during the periods of observation to provide context.

The four-month period of data collection will deliver 160 hours of detailed ethnographic observations, across the two hospital sites. Observation periods will be carried out over three days/shifts a week across their admission, providing approximately 20 hours per case study. Observational fieldnotes and in situ short interviews will be taken during observation periods and written up into more detailed data on the same day (producing approximately 175,000 words of data). No identifiable data (individual names, ward names, hospital name) will be recorded during data collection. All notes will use pseudonyms for patients and carers, and staff role only will be used in notes.

This will produce new understandings of how care is organised, adapted, and delivered for adults with learning disabilities during a hospital admission including how ward teams understand and respond to their needs.

Analysis

Data sets will be transcribed by JH into anonymised word documents or collected using handwriting software on a tablet and converted into Word files. Data will be checked and cleaned in Word. All tablets are provided by University of Southampton and password protected. These word documents will be entered into NVivo for analysis. The goal of analysis will be to create a conceptual model of how care is organised, adapted, and delivered for people with learning disabilities during a hospital admission via: (1) a narrative approach to deliver a series (n=8) of detailed case studies (interviews, observation, document analysis) that illuminate individual trajectories during an admission. This will illustrate the experiences of a range of people with learning disabilities across different clinical contexts, experiences, and outcomes. These case studies will be used to inform theory development to support and extend the ethnographic analysis of everyday care. They will also be used to inform output development including anonymised case scenarios.

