Written consent from the ward manager will be sought for attending meeting discussions about the patient's care. The researcher will ask for verbal consent from all staff in the meeting and if all staff do not agree, she will not take notes of their contribution. It is not practical to take consent from staff from other parts of the hospital as this may entail interrupting ward processes or interventions. Instead, posters giving information about observations on the ward will be prominently placed at the entrance to the room where observation of the patient is taking place. As described above, a note will be added to the patient's medical record to identify them as a participant in research, according to local standard research procedures. The researcher will carry information sheets and be available to answer questions and will take verbal consent from all staff when it does not interfere with clinical care processes or the work of the ward. An observation will be ceased should any staff member raise any concerns about being observed.

If the patient participant moves to another ward during data collection (including into an Intensive Care Unit or after moving onto an End-of-life care pathway), the researcher will explain the study to the new ward manager and seek initial verbal consent to continue the study on that ward if the patient participant (or on advice from a consultee) wishes to continue. She will check that the patient and their carers (if relevant) are happy to continue with the study on this new ward. She will then use the same recruitment and consent process for the ward manager and staff as described above, for this new ward.

RIGHT TO WITHDRAW

The participant will remain free to withdraw at any time from the study without giving reasons and without prejudicing his/her further treatment and will be provided with a contact point where he/she may obtain further information about the study. Participant withdrawal of consent from the study will be explicitly documented in the source documents.

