8.6 Data protection and patient confidentiality

All investigators and study site staff will comply with the requirements of the Data Protection Regulation and UK GDPR guidance with regards to the collection, storage, processing and disclosure of personal information and will uphold the Regulation's core principles. The PI will be the data custodian as part of her honorary contract with the sponsor, University Hospital Southampton NHS Foundation Trust. Participant details will remain confidential as per the requirements of the Data Protection Act (2018) and the University Hospital Southampton NHS Foundation Trust data management policy.

No identifiable data (individual names, ward names, hospital name) will be recorded during data collection. All notes will use pseudonyms for patients and carers, and staff role and ward speciality only will be used in notes. In all reporting and publication of findings individual participants will not be identifiable. Confidentiality will be ensured at all times. Patient pseudonyms (chosen by participants and agreed with the researcher to ensure they are not identifying) will be used for transcripts and in written reports. Direct quotes will not include any identifiable information. Methods of presentation that protect anonymity will be adopted including composite stories. In line with Caldicott Principles, only information necessary to the organisation and delivery of the study will be obtained from participants. This will be name (for consent forms) and name, email and address if patient or carer participants complete a request form to be sent a summary of the research findings (all documents with identifying details will be stored separately from their data).

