Linked anonymity will be guaranteed (each participant will be allocated an ID on entry to the study and code and participant list will be stored separately). The code sheet that links codes with individual identifying details will be stored on a password protected file on a password protected computer, and in a locked filing cabinet, separate to any research data storage. Any research data stored will be associated with individual codes not identifying details. All physical data will be stored in a locked cabinet at the University (paperwork) all electronic data on a password protected file on a network drive that is accessible only through the research team members' password protected accounts. This will only be accessed by members of the research team. Files relating to the project may sometimes be stored on researchers' local laptop disks, which are protected by a university login. However all sensitive files will be stored on the network drive where feasible, or if away from network access and access is critical, saved to the local laptop disk with a password known only to the research team. Data will be archived for 15 years in accordance with the University Hospital Southampton NHS Foundation Trust's Research Data Management Policy, and the CI will retain anonymised data from the study for use in further publications.

All information sheets and consent forms state that participants in the research are guaranteed anonymity. All contact details will be stored securely and destroyed after the final key output or summary document from the study is shared with prior participants. This data will play no part in any dissemination or outputs of the study and will be managed in line with UK General Data Protection Regulation

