9 DISSEMINATION POLICY

9.1 Dissemination policy

- Data belongs to University Hospital Southampton NHS Foundation Trust.
- Full study report will be completed in line with NIHR requirements and published as per their requirements, available on their site
- JH as CI holds rights to publications and will publish with co-applicants. No co-applicants can
 publish data independently of JH
- NIHR will be acknowledged in all outputs from the study as study funder following their guidance on wording
- All publications arising from this work will acknowledge the organisations involved in the research - University of Southampton, University of West London, University Hospital Southampton NHS Foundation Trust, Portsmouth Hospitals University NHS Trust, Southampton Mencap and Southern Health NHS Trust's Patient Experience Group.
- All patient participants will be asked when consented if they wish to receive a summary of the findings, and the best way to share this (e.g. postal address or email). If they wish to receive a summary, they will be given a separate form to complete, which will be stored separately from research data. We will share a summary of the research with patient and carer participants in appropriately accessible formats after our final data analyses have been completed, if they have agreed they would like this. We will also share a brief summary of the findings with both hospital sites and wards and key staff who have participated in the study, in addition to the outputs described elsewhere.
- The protocol will be made publicly available via the ISRCTN site
- · We will not be making our dataset publicly available

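### Section 8.6 guarantees anonymity without qualification, but with four openly observed patients per hospital the study cannot guarantee that ward insiders will not recognise a participant

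*Protocol*

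**What the plan says.** **The promise.** Protocol section 8.6 states: "All information sheets and consent forms state that participants in the research are guaranteed anonymity". The same section adds: "In all reporting and publication of findings individual participants will not be identifiable". Neither sentence carries an exception. The mechanism described is a code key: "Linked anonymity will be guaranteed (each participant will be allocated an ID on entry to the study", with the list linking codes to people stored separately.

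**The design.** The Study Summary (Planned Size of Sample) plans "8 adults with learning disabilities (4 per hospital"). Under section 7.3, the nurse in charge makes the first approach to the patient or carer, the researcher sits near the patient while observing, and the patient's medical record carries a research entry. Posters are "prominently placed at the entrance to the room where observation of the patient is taking place".

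**The analysis and outputs.** Section 5 (Analysis) plans "a narrative approach to deliver a series (n=8) of detailed case studies" and says these will inform outputs, including anonymised case scenarios. Section 4.2 plans output workshops with nursing staff of both hospitals and a masterclass at each site. Section 9.1 says the team will "share a brief summary of the findings with both hospital sites and wards and key staff who have participated" in the study.

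**The safeguards.** Sections 5 and 8.6 provide for pseudonyms, limited participant detail, no recording of individual, ward or hospital names, and presentation methods that include composite stories. On staff identifiers the two sections differ. Section 5 allows only the staff role in the notes; section 8.6 allows role and ward speciality.

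**The concern.** The guarantee covers all participants and all readers. In this study, however, some of the most interested readers were present when the data were collected. A pseudonym does not hide a patient from a nurse who watched the researcher at that bedside. A job title may not hide a specialist who is one of very few in the hospital. Nowhere does the protocol address recognition by people on the same ward, or provide for telling participants that it may happen.

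What is at stake is the accuracy of what people agree to. Patients and carers may describe poor care, and the accounts feed material that goes back to the hospitals concerned. Under section 7.3.2 a patient can withdraw data only during the data collection period. Someone who later recognises themselves in an output can no longer have the data removed, so the statement made at consent has to be right.

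**Working it through.** No power calculation applies, because this is a qualitative study without a hypothesis test. The check reproduces the sample figures and then compares the promise with the design.

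**1. The plan's own figures**
- Patients: 2 hospitals × 4 = 8, and 5% of the 160 eligible patients in section 7.2.1 = 8.
- Staff: about 8 per case (section 5) × 8 cases = 64.
- Total: 8 + 24 + 64 = 96 with the upper carer figure, and 8 + 16 + 64 = 88 with the lower one. The stated 96 reproduces at the upper figure.

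**2. How small the groups are for an insider**
- Patients in one hospital: 4.
- If those 4 are spread over 1, 2 or 4 wards (an assumption, as the protocol does not fix this), candidates per ward are 4/1 = 4, 4/2 = 2 or 4/4 = 1.
- Carers per case: 16/8 = 2 to 24/8 = 3. Recognising a case therefore narrows its carers to two or three people.
- Staff per case: about 8, recorded by role and, under section 8.6, ward speciality. Section 5 lists Learning Disability Liaison Nurses among the staff observed.

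**3. Promise against design**

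| What is promised | What the design does |
|---|---|
| Anonymity is guaranteed (8.6) | A code sheet links IDs to people (5, 8.6), so the data are pseudonymised |
| Nobody is identifiable in any reporting (8.6) | Participation is visible on the ward: nurse in charge, bedside researcher, posters, record entry (7.3) |
| Details are limited and composites used (5, 8.6) | Eight individual case studies feed scenarios (5), and no rule says which outputs must use composites |
| Staff appear by role only (5) | Staff appear by role and ward speciality (8.6) |
| Identifying details are kept apart from data (8.6) | Findings, workshops and masterclasses go to the same two hospitals (4.2, 9.1) |

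**4. Inference.** Recognition needs two things: knowing who took part, and an account with enough content to match to that person. Section 7.3 gives ward insiders the first. The second depends on how much individual content survives into the outputs. The protocol promises to limit that content but sets no rule that removes it. A guarantee needs the second to be impossible, and nothing in the text makes it so.

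**The case against.** The strongest reply is that known participation differs from identifiable reporting. Posters and a record entry show that someone took part; they do not tie a published account to that person. The individual case studies are listed under analysis, the wards are promised only a brief summary, and composites are a recognised protection against insiders as well as outsiders. Much of this stands. No section says that eight individual trajectories go to the wards, and the safeguards do reduce the risk. They still do not support an absolute promise, because the protocol does not say where composites are mandatory and the case studies are meant to feed scenarios.

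It is also fair that the information sheets are not available here, and that section 8.1 shows they carry at least one limit, the duty to report harmful care. Whether they also mention recognition cannot be checked. The point rests on what section 8.6 says all of them state.

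A reader might infer more than the documents support:
- **That anonymity fails towards everyone.** For outside readers, pseudonyms and limited detail may be enough.
- **That the planned sample is wrong.** The line giving four patients per hospital contains no error; it only supplies the small number.
- **That re-identification can be quantified** by dividing expected admissions by combinations of the sampling factors. This needs assumed factor levels, an even spread and full profiles in print. The protocol gives neither of the first two and promises to avoid the third.
- **That accounts will be biased towards favourable ones.** Nothing in the protocol supports a direction or size for such an effect.

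**Conclusion.** The point holds for insiders. Section 8.6 promises a property that the design can make likely but cannot guarantee towards ward staff, carers and others who know the participant. For them the group is at most four patients per hospital, and between four and one per ward if the four are spread over one to four wards; that spread is an assumption. The conclusion does not depend on it. It rests on the visible participation, the individual case studies and the return of material to the same hospitals, all of which are in the text.

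The size of the remaining risk cannot be calculated from the protocol, because it depends on how much individual detail the outputs keep. This is a should-fix matter of consent wording and output rules. It does not call the sample size, the fieldwork or the analysis into question.

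**What to change.** 1. **Section 8.6.** Replace the guarantee, and the sentence saying that nobody will be identifiable, with wording such as: *Data will be pseudonymised and personal details limited in all outputs. People involved in a participant's care, or who know them, may nevertheless recognise them.* Bring the matching statements in section 5 into line.
2. **Information sheets and consent forms.** Carry the same statement in each, including the accessible formats.
3. **Material returned to the two hospitals** (ward summaries, workshop and masterclass scenarios). Use only composites that mix cases from both sites, omit ward speciality, and merge small roles into a broader label such as specialist staff. State this rule in sections 4.2 and 9.1.
4. **Publications.** Do not attribute a case to a hospital. Section 9.1 names the organisations involved, two hospital trusts among them, so leaving the hospital out of the field notes is not enough.
5. **Staff identifiers.** Reconcile role only (section 5) with role and ward speciality (section 8.6).

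The cost is a less reassuring consent statement, some loss of local context in what the sites receive, and an amendment if the documents are already approved. Recruitment, data collection and analysis stay as planned.
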